### **6.1 Sample Size and Power Determination**

Power calculations were conducted using PASS (Version 21 NCSS), assuming a 5% type I error rate and using two-sided hypothesis tests. We used data collected in the AIRORA study performed at DLR to inform power calculations. With a proposed sample size of 24 subjects, we expect to have at least 80% power to detect a medium effect size of 0.60 for the mitigation effect of BN on our primary outcome due to aviation noise.

### **6.2 Statistical Methods**

The primary outcome of the study is: time spent in slow wave sleep (SWS) plus rapid eye movement (REM) sleep during an 8-hour sleep opportunity (11 pm – 7 am). We will use linear mixed effect regression models with random subject intercept to investigate whether SWS+REM duration differs significantly between the 6 study conditions (we will use non-linear mixed effect models for binary secondary outcomes). If  $p < 0.05$  of the omnibus test, we will perform post-hoc tests contrasting all conditions with each other. Our primary contrast of interest for which the study was powered is the difference in SWS+REM duration in aviation noise nights with and without broadband noise of 50 dB.

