## **3 Investigational Plan**

### **3.1 General Design**

Subjects will be screened in two screening sessions to determine study eligibility prior to participating in the in lab protocol. The sleep of 24 subjects will be monitored with polysomnography over 7 consecutive nights in groups of 4 where the entire group has been randomly assigned to 1 of 6 noise exposure condition patterns.

After an adaptation night, subjects will be exposed to:

1. Control night without any noise exposure and without earplugs (CTRL);
2. Aviation noise only (AN);
3. Broadband (pink) noise 50 dBA only (BN50);
4. Aviation noise plus earplugs (AN+EP);
5. Aviation noise plus broadband (pink) noise 40 dBA (AN+BN40);
6. Aviation noise plus broadband (pink) noise 50 dBA (AN+BN50).

We will investigate participants in 6 groups of 4 subjects each (we also plan for a reserve 7th study run to account for study drop-outs). Each group will be exposed to the same condition in each study night. Each subject will receive each exposure – in a randomized and balanced fashion – according to the randomization table in 3.2.

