### Noise Exposure

The AN nights will consist of up to 120 noise events with maximum sound pressure levels  $L_{AS,max}$  of 45, 50, 55, 60 and 65 dB, including noise from jet engine aircraft, helicopters, drones, and low sonic booms. The jet engine noise events will be identical to events used in a prior study at the German Aerospace Center (DLR) and another study on broadband sounds on sleep performed by collaborator [name] in Sweden, which allows for a direct comparison to these studies. We will choose a few events within each dB category and repeatedly play those back. Due to the limited sample size, playing every event back only once would not provide us with enough data for averaging. We will also include an alarm sound and/or sound of a baby crying, as a potential caveat of using EP/BN is that meaningful sounds may be missed. The sequence and spacing of noise events will be identical within a study group but different across study groups. Noise scenarios will be pre-programmed. They will be started at the next full minute after lights out. Planned lights out is 11 pm and planned lights on is 7 am (i.e., 8 hour sleep opportunity).

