### 3.2 Allocation to Interventional Group

We will investigate participants in 6 groups of 4 subjects each. Each subject of a group will be exposed to the same condition in each study night, and each subject will receive each exposure— in a randomized and balanced fashion – according to the randomization table below.

Group	Night 1	Night 2	Night 3	Night 4	Night 5	Night 6	Night 7
1	Adaptation	A	B	C	D	E	F
2	Adaptation	B	D	A	F	C	E
3	Adaptation	C	A	E	B	F	D
4	Adaptation	D	F	B	E	A	C
5	Adaptation	E	C	F	A	D	B
6	Adaptation	F	E	D	C	B	A

Please note that in this randomization paradigm, each exposure appears in each position exactly once, and is preceded by each other exposure exactly once. The letters A-F will be randomly assigned to the exposure conditions 1-6 listed in 3.1 above by the principal investigator using a random number generator. Study participants and staff will be blinded to the condition of each night. Staff will only be unblinded after the start of the measurements each night (i.e., after subjects went to bed) so that the correct playback of the conditions can be monitored.

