## **6 Statistical Plan**

We will perform similar analyses for the secondary outcomes. We will adjust for multiple testing using the false discovery rate method making sure that we keep the family-wise type I error rate at 5%. Multiple exploratory genetics analyses may be performed by FAA CAMI.

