#### **6.3.2 Analysis of Primary Outcome of Interest**

Our primary contrast of interest is the difference in SWS+REM duration in aviation noise nights with and without broadband noise of 50 dB. In the mixed model framework, this is equivalent to a paired t-test.

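### Conditions are assigned to groups of four per night, but the primary model has only a random subject intercept, so its validity rests on an unstated assumption of no shared group-night variation

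*Combined protocol and SAP*

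**What the plan says.** All references are to the combined protocol and SAP.

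**Assignment.** Section 3.1: "Each group will be exposed to the same condition in each study night". There are six groups of four and six exposure nights after adaptation. Section 3.2 sets the order by a 6x6 square in which "each exposure appears in each position exactly once, and is preceded by each other exposure exactly once".

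**Noise programme.** Noise Exposure in section 3.1: "The sequence and spacing of noise events will be identical within a study group but different across study groups", and "Noise scenarios will be pre-programmed". Staff are unblinded after bedtime "so that the correct playback of the conditions can be monitored" (section 3.2).

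**Analysis.** Section 6.2: "We will use linear mixed effect regression models with random subject intercept to investigate whether SWS+REM duration differs significantly between the 6 study conditions". An omnibus p below 0.05 opens all pairwise comparisons. The contrast of interest is aviation noise alone (AN) against aviation noise plus 50 dB broadband noise (AN+BN50), of which section 6.3.2 says: "In the mixed model framework, this is equivalent to a paired t-test". Section 6.3 adds age and sex and leaves other confounders open. No section names a night effect, a group-by-night effect, clustered standard errors or a degrees-of-freedom method.

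**Multiplicity.** Section 6, directly after a sentence on secondary outcomes: "We will adjust for multiple testing using the false discovery rate method", with the stated aim of holding family-wise error at 5%. Whether this reaches the post-hoc contrasts of section 6.2 is not clear.

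**Power.** Section 6.1 expects at least 80% with 24 subjects, effect size 0.60 and a two-sided 5% test.

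**The concern.** The unit that receives a condition is a group on a night, not a person. A random subject intercept absorbs stable differences between people, and with them stable differences between groups. The square balances any night effect common to all groups. Neither deals with variation specific to one group on one night. If such variation exists, the four differences within a group are correlated, the model's standard error is too small, and both the omnibus test and the unadjusted primary contrast reject too often. The omnibus test matters in its own right, because it opens the post-hoc comparisons.

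**Working it through.** **1. The plan's own power figure.** Reading 0.60 as the mean difference over the SD of the paired difference (section 6.1 does not define it), a paired t-test with n = 24 and 23 df has noncentrality 0.60 x sqrt(24) = 2.94 and power 80.4%. The subject-intercept model on 115 df gives 83.0%. So the stated 80% is reproduced, for 24 independent differences.

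**2. Error strata.** There are 24 x 6 = 144 observations, hence 143 df: 23 for subjects, 5 for condition and 115 residual. The residual splits into 25 df between group-nights (36 - 1 - 5 for groups - 5 for condition) and 90 df within them (6 groups x 3 x 5). The planned model pools the two.

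**3. Size of the understatement.** Let rho be the share of within-subject residual variance common to a group-night, beyond any night effect common to all groups. It is an assumption throughout. With residual variance 1:
- true variance of the contrast: 2(1 + 3 rho)/24
- variance the model expects: (2/24) x [25(1 + 3 rho) + 90(1 - rho)]/115

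At rho 0.10 the ratio is 1.30 / [(32.5 + 81)/115] = 1.30/0.987 = 1.317. Its square root is 1.15, so the true standard error is 15% above the model's.

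**4. Type I error.** Simulated on the protocol's square, which was checked: each condition once per position and all 30 ordered pairs once. Data were normal with equal variances and no missing nights; 100,000 trials per setting, 400,000 for the unadjusted contrast. Quiet nights are the control night and broadband noise alone. A shift of 0.85 residual SD equals 0.6 SD of the paired difference (0.6 x sqrt(2)).

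| % at rho = | 0 | 0.02 | 0.05 | 0.10 | 0.20 |
|---|---|---|---|---|---|
| True SE above model SE | 0 | 3 | 8 | 15 | 28 |
| Omnibus, no condition differs (approx.) | 5 | 6 | 9 | 13 | 23 |
| Primary contrast, no gate, no adjustment | 5.0 | 5.8 | 6.8 | 8.7 | 12.5 |
| Contrast after omnibus, no condition differs | 1.4 | 1.8 | 2.5 | 3.8 | 7.2 |
| Contrast after omnibus, quiet nights better by 0.4 residual SD | 3.5 | 4.2 | 4.9 | 6.7 | 10.3 |
| Contrast after omnibus, quiet nights better by 0.85 residual SD | 5.0 | 5.8 | 6.8 | 8.8 | 12.5 |
| Last row, with Benjamini-Hochberg over 15 contrasts | 2.3 | 2.8 | 3.6 | 5.0 | 7.8 |
| Omnibus, common trend of 0.15 residual SD per night | 3.6 | 4.7 | 6.4 | 10.3 | 19.4 |
| Contrast, same trend, no gate, no adjustment | 4.1 | 4.7 | 5.7 | 7.6 | 11.1 |

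The gate protects the contrast when no condition differs, but much less when quiet nights are truly better, which is the premise of section 1.1. A night trend common to all groups, left out of the model, enters the error term but not the balanced contrast, so it makes the tests conservative.

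**5. A group's shared reaction to noise.** A reaction common to all four of a group's aviation-noise nights (assumed variance 0.10, rho 0) leaves the contrast at 4.8%, because it cancels between AN and AN+BN50; the omnibus test is at 7.0%.

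**6. With a group-by-night term.** A fixed night effect takes 5 of the 25 df, leaving 20. With the variance unrestricted, simulated type I error of the contrast is 5.0 / 5.0 / 4.9 / 5.2 / 5.0% across the same rho values (60,000 trials). Power at 0.60 from the noncentral t with 20 df and noncentrality 0.60 x sqrt(24/(1 + 3 rho)) is 79.8 / 77.5 / 74.1 / 68.9% at rho 0 / 0.02 / 0.05 / 0.10.

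**The case against.** The strongest reply is that no documented source of rho is left. Stable group differences go into the subject intercept, and a common night trend makes the tests conservative. The shared noise sequence, on the natural reading of one programme per group, cancels in the primary contrast. Isolated bedrooms (section 1), private quarters (section 7.4.3), pre-programmed scenarios (section 3.1) and monitored playback (section 3.2) all point to a small value. This stands. A reader might infer from the group assignment and the shared noise sequence that the error rate is inflated; the documents do not show that, and nothing in them supports 0.10 or 0.20.

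A second reply is that the unadjusted, ungated contrast is not the whole planned procedure. This also stands in part: if section 6's adjustment covers the 15 post-hoc contrasts, the primary contrast is at or below about 5% through rho 0.10. It does not help the omnibus test, which comes before that adjustment.

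A third reply is that the night effect is not needed for validity and that a sensitivity analysis with a group-by-night term would be enough. The first half is right. But once the group-by-night term is in, an unmodelled common trend would be counted as group-night variance and widen the standard error. The second half would leave the gate and the main conclusion on the test that depends on rho, and six groups are too few to show that rho is zero: the variance estimate falls at or below zero in 53% of trials at rho 0 and still in 18% at rho 0.10.

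**Conclusion.** The omission is certain and its effect is unknown. The planned tests are valid if rho is zero. If rho is 0.02 / 0.05 / 0.10 and there is no offsetting common night trend, the omnibus test rejects about 6 / 9 / 13% of the time under no difference, and the primary contrast without multiplicity adjustment 5.8 / 6.8 / 8.7%. These figures rest on assumed rho values and on complete, normal, equal-variance data.

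Two further readings go too far. The stated 80% power is not wrong on its own inputs; it carries an assumption that section 6.1 does not state. Nor is the effective sample size six: it is 24/(1 + 3 rho), for example 18.5 at rho 0.10, and 24 if rho is zero.

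The plan should be changed because the analysis ought to respect the unit of assignment, the change is small, and it removes dependence on a quantity that the documents do not give.

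**What to change.** In sections 6.2 and 6.3.2, specify:

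> SWS+REM will be analysed with a linear mixed model with fixed effects for condition, night (2-7), age and sex, and random effects for subject and for group-by-night, with Kenward-Roger or Satterthwaite degrees of freedom. The group-by-night term is kept whatever its estimate; its variance is unrestricted and may be negative; the estimate is reported. A reserve run counts as its own group.

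Remove the paired t-test equivalence. The handling of the variance must be written down because it decides whether the test holds 5%. At rho zero, holding the variance at zero or above gives type I error 3.8% and power 78.3% if the term is dropped when zero (110 df), or 3.2% and 76.8% if the degrees of freedom stay near 20.

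In section 6.1, state that the 80% figure (80.4% for a paired t-test with n = 24 at 0.60) assumes no shared group-night variance, and give the power under the new model: 79.8 / 77.5 / 74.1 / 68.9% at rho 0 / 0.02 / 0.05 / 0.10.

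**Cost.** Wording, one variance component and one fixed factor; no more subjects. If rho is zero, power at 0.60 falls by 0.6 points from the paired t-test's 80.4%, or 3.2 points from the 115-df model's 83.0%, to 79.8%. That is slightly below the stated 80% and should be disclosed.

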### **3.4.2 Secondary Study Endpoints**

We plan to investigate the following secondary endpoints in relation to the different noise exposure conditions.

Sleep-related secondary endpoints:

1. Time spent awake and in different sleep stages (N1, N2, N3, REM)
2. Sleep fragmentation, i.e. number of awakenings and EEG arousals per hour sleep
3. Latency to sleep stages N2, N3 and REM
4. Frequency, density and amplitude of sleep spindles, K-complexes and vertex sharp waves
5. Power-spectral density in alpha, beta, theta and delta frequency bands
6. Event-related analysis with the following endpoints
  - a. Awakening
  - b. EEG arousal
  - c. Odds Ratio Product (ORP)

Non-sleep-related secondary endpoints:

1. Cognition test battery performance
  - a. One standard speed and one standard accuracy outcome for each of the 10 tests
  - b. Accuracy, speed and efficiency across cognitive domains
2. Driving simulator performance
  - a. Standard deviation of lateral position (i.e., continuous location of a vehicle with respect to a lane reference)
  - b. Standard deviation of speed
3. Hearing test
  - a. Threshold shift in dB at the following frequencies: 500 Hz, 1,000 Hz, 2,000 Hz, 4,000 Hz, 6,000 Hz, and 8,000 Hz
4. Blood test
  - a. Change in RNA expression levels

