### **6.3 Control of Bias and Confounding (if applicable, typically observational study or if randomization is not taking place)**

All statistical models by the Pennsylvania study team will be adjusted for age and sex. We will consider other relevant confounders depending on the investigated outcome variable. Genetics analyses by FAA CAMI may employ a variety of exploratory models.

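### Event-level random effects are not stated; with only the subject intercept of section 6.2, tests of overall countermeasure effects on awakening, EEG arousal and ORP would ignore night-to-night variation

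*Combined protocol and SAP*

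**What the plan says.** Section 6.2 gives the model for SWS+REM duration: "We will use linear mixed effect regression models with random subject intercept". A parenthesis in the same sentence adds "we will use non-linear mixed effect models for binary secondary outcomes", without naming random effects for them. Section 6 says "We will perform similar analyses for the secondary outcomes". Section 6.3 adds "All statistical models by the Pennsylvania study team will be adjusted for age and sex" and leaves room for further confounders chosen by outcome. No section names a random effect for night, group-night, recording or subject-by-source.

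Section 3.4.2 lists, among the secondary endpoints, "Event-related analysis with the following endpoints": awakening, EEG arousal and ORP. Section 2.2 asks whether aviation sources differ in how strongly they arouse sleepers, and whether BN and EP differ in how well they mitigate the different kinds of noise.

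On the design, section 3.1 says "Each group will be exposed to the same condition in each study night". By the table in 3.2, each subject has one night per condition. Under Noise Exposure, section 3.1 says "The AN nights will consist of up to 120 noise events" and "We will choose a few events within each dB category and repeatedly play those back".

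**The concern.** A subject intercept suits the primary outcome, where each subject gives one value per night. At event level the same structure leaves out a layer. A subject who sleeps lightly on a given night will tend to react to more of that night's events, whatever the condition. Because each condition is one night per subject, that night effect cannot be separated from the condition effect within a subject. A model with only a subject intercept counts up to 120 correlated responses as independent evidence on a factor applied once. Age and sex are constant within a subject and cannot absorb this.

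Source comparisons are made within nights, so night variation largely cancels from them. They have their own missing layers: subjects may differ in their response to, say, helicopters relative to jets, and a few recordings stand for each source.

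At stake is a claim that BN or earplugs reduce event-related awakenings, arousals or ORP, or that one source is more arousing than another, made more often than the nominal level allows. A multiplicity adjustment takes its p-values as valid and does not repair ones that are too small.

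**Working it through.** **Inputs from the documents.** 24 subjects and a two-sided 5% level (6.1); up to 120 events per aviation-noise night, five levels, four aviation sources (3.1); six groups of four, one night per condition (3.2).

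**Assumptions, since the documents give no variances.** 10% awakening probability, subject SD 0.5 logit, even split of events over sources and levels, no true effect. The other SDs are varied.

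**1. The plan's own figure.** Paired t-test, n = 24, effect size 0.60 read as mean difference over SD of differences: noncentrality 0.60 × √24 = 2.94, df 23, power 0.804. The stated 80% reproduces. It concerns the nightly primary outcome, where the residual already contains subject-by-night variation.

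**2. ORP, closed form.** With m events per night and night share ρ of within-subject variance, the design effect is DE = 1 + (m − 1)ρ, and the actual type I error is 2 × (1 − Φ(1.96/√DE)).

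| m | ρ | DE | Type I error |
|---|---|---|---|
| 120 | 0.005 | 1.59 | 12% |
| 120 | 0.01 | 2.19 | 18.5% |
| 120 | 0.02 | 3.38 | 29% |
| 60 | 0.005 | 1.29 | 8.5% |
| 60 | 0.01 | 1.59 | 12% |
| 60 | 0.02 | 2.18 | 18% |

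At ρ = 0.01, m = 20 gives 7% and m = 5 gives 5.5%. The alarm and baby-cry contrasts, whose event numbers are not stated, are therefore little affected if such events are few.

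**3. Awakening, one countermeasure contrast, 120 events, simulated.**

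| Night SD (logit) | 0 | 0.1 | 0.2 | 0.3 | 0.5 |
|---|---|---|---|---|---|
| Subject-stratified test, 20,000 trials | 4.9% | 6.6% | 11.5% | 18.3% | 35.4% |
| Logistic model, subject intercept, 1,000 trials | 4.7% | 7.3% | 10.4% | 17.6% | 36.0% |
| Same model, separate code, 600 trials | 5.2% | 7.3% | 10.5% | 18.5% | 32% |
| With subject-by-night intercept, 1,000 trials | 4.1% | 6.3% | 5.4% | 6.2% | 6.7% |

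With 60 events the stratified test gives 5/6/8/12/23%. A paired t-test on one summary per subject-night stays at 4.5–5.2% when no group-night variation is simulated.

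**4. The omnibus gate of 6.2.** At the same night SDs, the 3-df test over the four aviation-noise nights runs at 5.7/6.8/14.5/32/61%. A single contrast that must first pass this gate rejects in about 2/3/6/14/31% of null trials, before any multiplicity adjustment.

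**5. Source main effects, 120 events, one pairwise contrast.** With three recordings per source and level and recording SD 0.1/0.2/0.3/0.5, the error is 6/7/10/18% using the AN night alone and 7/13/24/42% pooling four aviation-noise nights. A second pooled run gave 4/13/27% at SD 0.1/0.2/0.3 with three recordings and 14/30/40% with one (300 trials per setting, error up to 3 points). Subject-by-source SD 0.1/0.2/0.3 gives 5/7/8% (AN alone) and 7/11/18% (pooled). Night SD 0.5 alone leaves the source test at 4–6%.

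**6. Source-by-countermeasure interaction.** This is a difference of within-night source differences. Night intercepts cancel within nights; recording and subject-by-source intercepts cancel between nights. With only those components (SDs up to 0.5) the test holds at 4.5–5.5%. With subject-by-source-by-night SD 0.2/0.3/0.5 it runs at about 6/9/15%, and with recording-by-condition SD 0.1/0.2/0.3 at 6/7/9%. The second could arise if broadband noise masks some recordings more than others.

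**7. Group-night.** Four subjects share each night's condition and event sequence. With night SD 0.2 and group-night SD 0.1/0.2/0.3, even the paired t-test on subject-night summaries runs at about 7–8/13/18%.

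**The case against.** The strongest reply is that this is silence, not a stated error. The subject intercept is written for the nightly primary outcome, where it is adequate; for binary secondary outcomes the plan names no random effects; and similar does not mean identical. An experienced team might add a night term unprompted. All of that stands, so the point is conditional. But the parenthesis on binary outcomes sits in the sentence that names the subject intercept, and the clearly binary outcomes in 3.4.2 are the event-level ones. A literal reading leads to the subject-only model.

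Two further replies stand in part. The rates in step 3 are for one ungated, unadjusted contrast; the gate brings the contrast to about 3–6% at night SD 0.1–0.2. It does not remove the problem, because the omnibus test is itself inflated. And recording variation counts as error only if conclusions are meant to reach beyond the recordings played; that is a matter of inferential scope.

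A reader might infer that the plan prescribes a faulty event-level model, or that its false-positive rate is 18% or 35%. The documents support neither: they state no such model and give no variances. A reader might also infer, in the other direction, that the interaction in 2.2 is safe. That holds only if source-by-night and recording-by-condition variation are absent, and the documents do not settle this.

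**Conclusion.** The point holds as a conditional one. If the single random effect named in 6.2 is carried to event-level data and night variance is not zero, tests of overall BN and earplug effects on awakening, arousal and ORP reject too often: about 7/11/18/35% for one ungated, unadjusted contrast at night SD 0.1/0.2/0.3/0.5 and 120 events, less with fewer events or behind the gate, and 5% at zero variance. Source main effects are too precise under subject-by-source variation, or under recording variation if general statements about sources are intended; the size depends on the unstated number of recordings. The interaction is robust to some components and not to others.

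The point does not extend to the primary analysis or its 80% power, since there the residual carries subject-by-night variation. Confidence is medium: the mechanism follows from the design, but every size rests on assumed variances. The crossed-effects model suggested below for source contrasts was not itself fitted. In its place, two-way clustering by subject and recording was simulated and gave 2.5–4.9%.

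**What to change.** In 6.2, state the event-level model separately from the nightly one.

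- **Overall countermeasure contrasts:** add a subject-by-night random intercept, or analyse one summary per subject-night. In either case include a group-night random effect or report sensitivity to it. With six groups there are only six pairs of group-nights per contrast, so this variance will be poorly estimated.
- **Source contrasts:** add a subject-by-source effect, plus a recording effect unless conclusions are limited to the recordings played. State the number of recordings per source and level, and whether the contrast uses the AN night only or all aviation-noise nights.
- **Source-by-countermeasure interaction:** include a subject-by-source-by-night term, and say whether the BN/EP clause in 2.2 means this interaction or an overall effect.

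The cost is wording, a heavier model and somewhat wider intervals; no new data are needed. In the awakening simulation at 120 events and an odds ratio of 0.7, power with and without the subject-by-night term is 97% and 97% at night SD 0, and 80% and 91% at SD 0.3, where the 91% comes with about 18% type I error. Subject-night summaries give 91–96% and 71–74% at those two SDs. These power figures include no group-night variation.

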### **2.1 Primary Objective**

The primary objective of this study is to investigate whether BN exposure at two intensities or wearing earplugs mitigates the negative consequences of aviation noise on sleep.

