### 4.2 Total Number of Subjects and Sites

The enrollment goal of the study is N=24 subjects with completed evaluable data. However, if a subject withdraws or is withdrawn from an in-laboratory study run, we will need an additional back-up run(s), each of up to n=4 individuals to account for the loss of data. Therefore, it is expected a total of N=28 subjects may begin the in-lab phase, thus allowing for completed evaluable data on up to ~n=27 subjects. Recruitment is expected to end when approximately 84 subjects have been screened. It is expected that approximately 84 subjects will need to be screened in order to enroll 24 evaluable subjects. The University of Pennsylvania is the only site enrolling participants for this research protocol.

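### Section 6.2 makes every pairwise contrast depend on a significant six-condition omnibus test and does not exempt the primary one (AN+BN50 versus AN), while section 6.3.2 gives that contrast with no such condition

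*Combined protocol and SAP*

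**What the plan says.** Section 6.2 fits a linear mixed model with a random subject intercept to time in slow wave plus REM sleep over the six conditions. Given p < 0.05 "of the omnibus test, we will perform post-hoc tests contrasting all conditions with each other". The next sentence reads: "Our primary contrast of interest for which the study was powered is the difference in SWS+REM duration in aviation noise nights", comparing nights with 50 dB broadband noise added against nights without. It gives this contrast no test of its own and does not take it out of the set just described.

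Section 6.3.2, on the primary outcome, names the same contrast, mentions no omnibus test and adds: "In the mixed model framework, this is equivalent to a paired t-test".

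Section 6.1 works "assuming a 5% type I error rate and using two-sided hypothesis tests" and states: "With a proposed sample size of 24 subjects, we expect to have at least 80% power to detect a medium effect size of 0.60". It names no test, no scale for the 0.60 and no broadband level, and mentions neither an omnibus condition nor a pairwise adjustment.

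The multiplicity sentence in section 6 (false discovery rate method, family-wise error at 5%) comes directly after "We will perform similar analyses for the secondary outcomes". It most naturally covers only those outcomes, but it does not say that the primary contrast is outside it.

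**The concern.** Two analysts could follow the plan faithfully and disagree on whether the primary test is done. If the omnibus p-value is above 5%, the reader of 6.2 stops, while the reader of 6.3.2 goes on to test AN+BN50 versus AN. A 5-df test can miss a real single-pair difference when the other four conditions add little spread.

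Two things are at stake. The decision rule for the one powered comparison is not fixed in advance. And if 6.2 is followed, the power in 6.1 may not describe the procedure actually used.

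**Working it through.** **Inputs.** n = 24, two-sided 5%, effect 0.60 and power of at least 80% are from 6.1. The six conditions are from 3.1 and give 6 × 5 / 2 = 15 pairs. Assumptions: 0.60 is the mean paired difference divided by the SD of the paired differences, and the data are balanced with compound symmetry and independent subjects.

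**Step 1: the plan's own figure.** The noncentrality is 0.60 × √24 = 2.94.
- Paired t-test, 23 df: power 80.4%. With 23 subjects it is 78.5%, so 24 is the smallest n that reaches 80%.
- Contrast from the mixed model, (6 − 1) × (24 − 1) = 115 df: power 83.0%.

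The stated 80% is therefore reproduced by the stand-alone test on this scale. If 0.60 is instead on the raw SD, the paired-t power is 66%, 80% or 95% for a within-subject correlation of 0.3, 0.5 or 0.7.

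**Step 2: power under the literal 6.2 rule.** Both the omnibus F(5, 115) and the contrast must be significant. Place AN at 0 and AN+BN50 at 1. With residual variance σ², the squared gap is 0.60² × 2σ² = 0.72σ². The omnibus noncentrality is 24 × 0.72 × SS = 17.28 × SS, where SS is the sum of squared deviations of the six positions from their mean. The other four positions are not in the documents and are assumed.

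For control at c and broadband noise alone at b, SS is smallest when earplugs and BN40 both sit at (1 + c + b)/4. Then SS = 1 + c² + b² − (1 + c + b)²/4. If c and b are each at least 1, so that nights without aircraft noise are no worse than AN+BN50, the minimum is at c = b = 1: SS = 3 − 9/4 = 0.75 and noncentrality 17.28 × 0.75 = 12.96.

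Power for both tests together was simulated (200,000 trials per row). The noise effect is the control position × 0.60.

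| CTRL / BN50 alone / AN+EP / AN+BN40 | Noise effect, CTRL vs AN | Noncentrality | Omnibus power | Both significant, % (model / paired t) |
|---|---|---|---|---|
| 2 / 2 / 1 / 0.5 | 1.20 | 55.4 | 1.00 | 83 / 80 |
| 1.5 / 1 / 0.75 / 0.5 | 0.90 | 22.5 | 0.965 | 82 / 79 |
| 1.33 / 1.33 / 0.92 / 0.92 | 0.80 | 20.6 | 0.949 | 81 / 79 |
| 1.25 / 1 / 0.81 / 0.81 | 0.75 | 15.9 | 0.871 | 77 / 75 |
| 1 / 1 / 1 / 1 | 0.60 | 14.4 | 0.830 | 75 / 73 |
| 1 / 1 / 0.75 / 0.75 | 0.60 | 12.96 | 0.782 | 72 / 70 to 71 |

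Against 83.0 / 80.4 for the stand-alone test, the loss runs from nothing to about 11 points (model) or 10 points (paired t).

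**Step 3: type I error under the global null.** Omnibus significant 5.0%; primary contrast significant 5.0%; both 1.4%. Either one: 5.0 + 5.0 − 1.4 = 8.6% (8.6 to 8.7% over simulations).

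**The case against.** The strongest reply is that the documents already answer the question. Section 6.2 singles out the contrast right after the post-hoc sentence, and 6.3.2 gives it its own analysis. That is probably the intent. It stands as a reading, but neither section says so, and the literal rule in 6.2 covers all pairs.

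Four stronger readings are tempting, and the documents do not support them.

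- *The 80% proves a stand-alone test was planned.* It does not. In the first row of the table the conditional rule also gives 83% / 80%. Section 6.1 leaves the test, the scale and the broadband level open, and the prior study that informed it is not in the documents.
- *The rule penalises a countermeasure that works.* The table holds the AN to AN+BN50 gap at 0.60, so its low rows are those where aircraft noise itself does little. Fix the noise effect at 0.80 instead, with broadband noise alone level with control and earplugs and BN40 placed to minimise omnibus power. Power under the rule (model contrast) then rises from 49% at half restoration to 95% at full restoration, with a loss of about 2 points at most.
- *Choosing the rule after seeing results inflates type I error.* A rejection under the conditional rule is always also a rejection by the stand-alone test, so the primary contrast's error cannot exceed 5%. What remains is an unfixed decision rule.
- *The loss could be far larger.* Power falls to about 57% if all four other conditions lie midway between AN and AN+BN50. That requires silence to be worse for sleep than aircraft noise plus broadband noise.

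The protocol's premise that aircraft noise disturbs sleep (1.1) favours the low-loss end.

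**Conclusion.** The conflict between 6.2 and 6.3.2 is real and should be resolved before analysis. As written, 6.2 can withhold the one comparison the study was powered for.

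The possible cost is modest and rests on assumptions. It is near zero if aviation noise lowers the outcome against control by clearly more than 0.60. It is up to about 10 or 11 points (72% model, just over 70% paired t) if the noise effect is only about 0.60 and control is about level with AN+BN50. This takes 0.60 as the standardized paired difference, compound symmetry, and four condition means that the plan does not supply.

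A reader might infer that the trial is underpowered or that its error rate is inflated. Neither follows: the stand-alone test supports the stated 80% on this scale without any change in n.

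**What to change.** State in 6.2 and 6.3.2 that AN+BN50 versus AN is the single primary test, done at two-sided 5% whatever the omnibus result and outside the false discovery rate adjustment of section 6, and that the omnibus condition applies only to the other 14 pairs. State the scale of the 0.60 in 6.1 at the same time.

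If the omnibus condition is meant to cover the primary contrast, keep it, but restate the power in 6.1 for that rule with all six assumed condition means. In the two lowest rows of the table, 80% would take 27 to 29 subjects, depending on row and test. The target is 24, with 4.2 "thus allowing for completed evaluable data on up to ~n=27 subjects"; that figure is an expectation, since further back-up runs are allowed.

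The first option costs a few sentences and no data. Its statistical price is that, under the global null, the chance that either the primary contrast or the omnibus test is significant becomes about 8.6 to 8.7% instead of 5%. The primary contrast's own error is the planned 5%, against about 1.4% under the conditional rule. The text should make clear that the 5% family-wise statement in section 6 does not span both tests.

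There is also a trade-off for the sponsor. The primary objective in 2.1 asks "whether BN exposure at two intensities or wearing earplugs mitigates the negative consequences of aviation noise on sleep", so how earplugs and the 40 dBA level rank against the single primary test is the sponsor's decision.
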